4.4 Statistical Design and Power

Participants

Testing Participants: participants will endorse opioid or other substance abuse in the past 6 months, and must speak English or Spanish; they will be clients at either Argus or Alliance or recruited via chain-referral or credible messenger strategies.

Staff/Credible Messenger Participants will be currently employed at either Argus or Alliance, including Credible Messengers. N=500 testing participants and n=20 staff will be recruited. Main study outcome data are to be drawn from study developed testing database and form participant and staff surveys.

4.4.1 Primary data analysis overview

Primary data analysis overview.

1. Examine and compare the efficacy of two sets of implementation strategies on (i) reach, (ii) testing uptake, (iii) service delivery (i.e. quarantine, medical care, contact tracing) and (iv) sustainability for individuals who use opioids and other drugs. Use of data drawn from Healthix, a public health information exchange, will supplement this comparison by generating a baseline of participant prior testing and health behavior to determine access to underserved populations as well as longterm influence on future testing behavior
 - a) **We hypothesize** that chain-referral will demonstrate better (i) reach, (ii) testing uptake, (iii) service delivery and (iv) sustainability compared to credible messenger.
 - b) **Analytic approach:** For our primary (dichotomous) outcome the form of the logistic model will be used to examine the differences in testing uptake (reach, service delivery and sustainability) between credible messenger an chain-referral.
- 2) Elucidate and compare the *system/organizational-, staff-, and individual-level factors that influence implementation (i.e. fidelity, acceptability, feasibility, sustainability) of the strategies* to develop a plan for

dissemination and scale-up in other CBOs who serve opioid and other substance using individuals in NYC.

- a) **Example hypothesis:** As an illustrative example, we hypothesize that housing instability will be negatively associated with testing uptake.
- b) **Analytic approach.** Implementation features related to acceptability, sustainability, feasibility, and fidelity will be assessed at both the staff- and individual-level. The logistic model will take the form $\text{logit}(\text{pi}) = \beta_0 + \beta_{\text{RecStr}}(\text{Recruitment Strategy})_i + \beta_{\text{Site}}(\text{Site})_i + \beta_{\text{TimeCon}}(\text{Time Constraint})_i$ where pi is the probability of being tested post-recruitment for the i^{th} individual. This model assesses the effect of a time barrier on the likelihood of getting testing while controlling for the differing recruitment strategies and sites.

Consortium Data Reporting. We will use our existing protocols for data checking, cleaning, and data editing and/or will rely on those proposed by the Coordination and Data Collection Center (CDCC) as relevant to ensure that collected data are clean and in compliance with confidentiality protections (e.g., de-identified) before they are forwarded to the CDCC for pooled analysis. We commit to providing the CDCC with timely, accurate data on number of tests conducted, their results, and subsequent actions taken. We will also provide data on effective implementation recruitment strategies to facilitate dissemination across the broader consortia.

4.5 Statistical Analyses

4.5.1 Analysis overview and main outcomes. The primary outcome of interest comparing the strategies will be testing occurrence (yes vs. no) as an indicator of testing uptake. An important secondary outcome will be reach measured through the number of coupons redeemed. Prior to the main analysis, all variables will be examined for distribution and outliers. Continuous outcomes will be described through means and standard deviations, while dichotomous and categorical outcomes will be described through proportions.

4.5.2 Statistical analysis for Aim 2. Models that compare the effect of recruitment strategy on outcomes related to reach, testing uptake, and service delivery will adjust for measures assessed at baseline (e.g., baseline substance use, testing history). For our primary (dichotomous) outcome (testing uptake) logistic regression will be used: $\text{logit}(\text{pi}) = \beta_0 + \beta_{\text{RecStr}}(\text{Recruitment Strategy})_{ii} + \beta_{\text{Site}}(\text{Site})_{ii} + \beta_{\text{SubUse}}(\text{Substance Use})_{ii} + \beta_{\text{TestHis}}(\text{Testing History})$, thus be β_{RecStr} which will estimate the differential effect of chain-referral vs. POL recruitment on testing uptake. The model will be adapted for secondary outcomes. Sensitivity analyses will stratify the analyses by time to determine if recruitment strategy effects differed before and after the cross-over. Demographic characteristics and other variables related to the Andersen, SCT, and EPIS models will be examined as potential mediators/moderators.

4.5.3 Statistical analysis for Aim 3. Implementation features related to acceptability, sustainability, feasibility, and fidelity will be assessed at both the staff- and individual-level. As an illustrative example, we will consider whether participants endorse time constraints and the association with testing uptake. The logistic model will take the form $\text{logit}(\text{pi}) = \beta_0 + \beta_{\text{RecStr}}(\text{Recruitment Strategy})_{ii} + \beta_{\text{Site}}(\text{Site})_{ii} + \beta_{\text{TimeCon}}(\text{Time Constraint})_{ii}$ where pi is the probability of being tested post-recruitment for the i^{th} individual. This model assesses the effect of a time barrier on the likelihood of getting testing while controlling for the differing recruitment strategies and sites.

4.6. Subject participation duration:

N/A

4.7. FDA regulated intervention:

No

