Social network strategies effective at identifying hidden populations and improving access to HIV related services may improve uptake of COVID-19 testing. Social network interventions utilize existing patterns of relationships to accelerate behavior change have been successful in increasing the uptake of HIV testing among marginalized populations, including people who use drugs. Moreover, social network approaches successfully counter stigma, medical mistrust, and misinformation around HIV, making them uniquely suited for addressing similar issues in the context of COVID-19. Two distinct social network recruitment strategies, chain-referral and Popular Opinion Leader (POL or “credible messenger”) models may be promising for increasing rapid COVID-19 testing. In chain-referral a discrete number of “seeds” are identified and incentivized to refer members of their social networks, who in-turn repeat the process. In POL models, popular and socially influential individuals with lived experience are trained to engage within formal and informal social networks to promote behavior change. Based on the efficacy of chain-referral and POL recruitment in the context of the HIV/AIDS epidemic, the success of these strategies to promote COVID-19 testing in underserved populations of substance users is highly plausible. Given the distinct differences of these strategies, it is important to contrast them to determine the comparative benefits of one approach over the other.

Ongoing quality improvement (QI) to promote an adaptive response to an evolving epidemic and promote sustainability. Plan-do-study-act (PDSA) is an evidence-based, rapid-cycle change model for testing enhancements on a small scale before incorporating them on a larger scale. Training staff, and POLs to use data (e.g. testing uptake, client feedback) to monitor and improve program performance may be a useful tool to develop sustainable strategies that address a rapidly changing pandemic as well as incorporate new testing, treatment and prevention (i.e., vaccine) technology.

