We will examine the impact of the intervention on (i) reach, (ii) testing uptake and (iii) service delivery (i.e. quarantine, medical care and contact tracing among COVID-19 positive cases); and (iv) sustainability for individuals who use opioids and other drugs as well as potential mediating/moderating variables from the Andersen, SCT and EPIS models. Data drawn from Healthix on prior and future COVID-19 testing will augment study data to determine access to underserved populations and influence on future testing behavior. RAs will conduct interviews in private rooms at Argus and Alliance. Participants will be assured that responses are confidential (see Human Subjects). Interviewers will be trained with established protocols, covering informed consent, confidentiality, reporting requirements, interview content, and cultural sensitivity.

End-of-Study Definition

This study will be stopped prior to its completion if: (1) the intervention is associated with adverse effects that call into question the safety of the intervention such as increased rates of COVID-19 infection; (2) difficulty in study recruitment or retention, or enrollment of participants will significantly impact the ability to evaluate the study endpoints; (3) any new information becomes available during the trial that necessitates stopping the trial; or (4) other situations occur that might warrant stopping the trial.

Human Subjects Characteristics

Setting. Participants will be recruited from Washington Heights, Harlem two neighborhoods in northern Manhattan, the Lower East Side, a neighborhood in southern Manhattan, and the South Bronx, the locations and geographic catchment areas of Argus and Alliance. In addition to current demographics of their current

substance using clientele, we anticipate participants will comprise 64% male, 51% African American, 39% Hispanic.

Randomization. Just prior to the onset of Phase 2, the chain referral strategy will be randomly assigned (50:50) to a clinic in order to begin the first roll out. After the initial roll out and plan-do-study-act cycle (PDSA), the assignment will be switched such that the chain referral is then implemented at the other site.

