
4.2. Sample Size Determination

Power calculations assume that we will be able to recruit 500 participants in total (250 recruited in each strategy) for this supplement study over Phases 2a and 2b. We also assume alpha (type I error rate) of 0.05. Our primary outcome of interest is testing occurrence. Based on zip-code level testing data, the average baseline testing in the communities of interest (i.e., northern Manhattan, the Bronx) is 7842.2/100,000. If we assume that one of the methods of recruitment will have a testing rate similar to this baseline average, we will have > 80% power to detect an approximately 8 percentage point difference in testing among the recruitment strategies (7.8% vs. 16.1%) corresponding to an odds ratio of 2.27, a moderate effect size.

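### The primary Aim 2 model of the two-site cross-over has no period term, so a change in uptake over time biases the strategy effect whenever the two sites carry unequal weight.

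*Combined protocol and SAP*

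**What the plan says.** **Design.** The Justification for Intervention (section 3.1.1(a)) describes a cross-over at two community organisations, with the starting strategy drawn at random and run for 4 months. The Randomization paragraph of the same section adds: "After the initial roll out and plan-do-study-act cycle (PDSA), the assignment will be switched". The Justification presents the quality-improvement cycle (PDSA) as a possible means to "develop sustainable strategies that address a rapidly changing pandemic as well as incorporate new testing, treatment and prevention (i.e., vaccine) technology".

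**Primary model.** Section 4.5.2 states: "Models that compare the effect of recruitment strategy on outcomes related to reach, testing uptake, and service delivery will adjust for measures assessed at baseline". The logistic equation that follows has four terms: recruitment strategy, site, substance use and testing history. The Aim 3 model (4.4.1 and 4.5.3) has strategy, site and time constraint. There time constraint means a barrier the participant reports, not calendar time.

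**Time.** Section 4.5.2 also plans sensitivity analyses stratified by time, to see whether the strategy effect differed before and after the switch.

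**Numbers.** Section 4.2: "Power calculations assume that we will be able to recruit 500 participants in total (250 recruited in each strategy"). No enrolment target is given by site or by site and period. Section 2.5 gives both sites the same starting resources: 8 seeds and 4 credible messengers each.

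**The concern.** Within a site, strategy and period are the same comparison, because the site runs one strategy in the first half and the other in the second. At one site chain referral comes first; at the other it comes second. Any change in willingness to test between the halves therefore adds to the chain-referral effect at one site and subtracts from it at the other. The two contributions cancel only if the sites have equal weight in the fit. Site enrolment is not fixed by the design, since recruitment (reach) is itself an outcome.

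If the contributions do not cancel, part of a time trend is reported as a difference between strategies. Its direction depends on which site enrolled more and which strategy that site drew first. Phase 3 implements the strategy found efficacious and section 4.8 plans to scale it up, so the choice could be swayed by the calendar.

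**Working it through.** **1. The plan's own figure.** Inputs from section 4.2: 250 per strategy, alpha 0.05 (taken as two-sided), 7.8% vs 16.1%. The pooled proportion is (0.078 + 0.161)/2 = 0.1195.

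- Null SE = √(2 × 0.1195 × 0.8805/250) = 0.0290.
- Alternative SE = √((0.078 × 0.922 + 0.161 × 0.839)/250) = 0.0288.
- Power = Φ((0.083 − 1.96 × 0.0290)/0.0288) = Φ(0.908) = 81.8%.
- Odds ratio = (0.161/0.839)/(0.078/0.922) = 2.27.

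Both stated figures reproduce. The calculation is for two independent groups and contains neither site nor period.

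**2. The layout.** Let site A start with chain referral (CR) and site B with credible messenger (CM). Let τ be the strategy effect and π the period effect, both on the logit scale.

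| | First half | Second half | CR minus CM within site |
|---|---|---|---|
| Site A | CR | CM | τ − π |
| Site B | CM | CR | τ + π |

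A model with site but no period pools the last column with weights w ≈ n₁n₂/(n₁ + n₂), where n₁ and n₂ are the two halves of a site:

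estimate ≈ τ + π × (w_B − w_A)/(w_A + w_B).

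With equal halves in each site, the multiplier is (n_B − n_A)/N: 0 at 50/50, −0.20 at 60/40, −0.30 at 65/35 and −0.40 at 70/30.

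**3. Does the strategy target protect?** No. At 350/150 by site with equal halves, chain referral has 175 + 75 = 250 participants and credible messenger has 175 + 75 = 250.

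**4. Size of the bias with no true strategy effect.** Assumed: period odds ratio 2.27 (the plan's target strategy effect, used only as a yardstick), 500 independent participants, and the larger site starting with chain referral. ln 2.27 = 0.820. The approximation gives exp(−0.20 × 0.820) = 0.85, exp(−0.30 × 0.820) = 0.78 and exp(−0.40 × 0.820) = 0.72. A logistic fit of strategy + site to the expected cell counts at a 7.84% first-half rate gives 0.85, 0.79 and 0.73. If the smaller site starts with chain referral, these invert.

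**5. False-positive rate.** With z = ln(OR)/SE, the rate is Φ(z − 1.96) + Φ(−z − 1.96). For 65/35 at 7.84%: z = ln(0.788)/0.276 = −0.863, giving about 14%.

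| First-half uptake | Period OR | 50/50 | 60/40 | 65/35 | 70/30 |
|---|---|---|---|---|---|
| 7.84% (section 4.2) | 2.27 | 5% | 9% | 14% | 21% |
| 7.84% | 1.5 | 5% | 6% | 7% | 8% |
| 50% (assumed) | 2.27 | 5% | 14% | 26% | 42% |
| 95% (assumed) | 2.27 | 5% | 6% | 8% | 10% |

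With a period term the expected odds ratio is 1.00 and the rate 5% in every cell.

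**6. With a true effect.** Take a true odds ratio of 2.27, a period odds ratio of 2, sites 350/150 and the 7.84% rate. The stated model then expects 1.71 (simulated power 59%) if the larger site starts with chain referral, or 2.95 if the smaller one does. With period added it expects 2.27, with simulated power of 82–84%.

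**7. The stratified analysis.** Within one half, each site runs a single strategy, so strategy and site are the same variable. The section 4.5.2 model cannot be fitted with both terms, and without site the contrast mixes strategy with site.

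**The case against.** The plan does not ignore time, and a reader who looked only at the equation might infer that it does. The stratified analysis is there and has some use. If the two stratum contrasts are run without a site term and averaged with equal weight, a period effect drops out within each stratum and a constant site effect drops out across them on the logit scale. But the plan does not say to average them. The stated purpose is to look for a difference in effect, and the primary estimate stays as it was.

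The second objection is that the harm may be small. Seeds and messengers are equal by site, and nothing in the documents points to a 65/35 or 70/30 split. Section 2.5 says the test is offered straight after the assessment, and section 3.1.1(b) has it delivered at the end of the survey, so uptake among those enrolled may be close to 100%. This stands. At 95% uptake the rates are 6%, 8% and 10%, and the 42% figure needs mid-range uptake together with a large period change and a 70/30 split.

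Third, one might infer that the plan predicts a change in uptake, or that the cross-over was adopted to remove time trends. The documents support neither. PDSA is described only as potentially useful for improving performance, and no reason is given for choosing a cross-over.

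**Conclusion.** The gap is real: the primary Aim 2 equation omits period in a two-period design with an improvement cycle before the switch, and the planned sensitivity analysis does not repair the primary estimate. The bias requires both a change in uptake between the halves and unequal site weights; with equal sites it is zero. The documents give neither a site split nor a period change, so the period odds ratios, splits and uptake levels other than 7.84% are assumed ranges, and independence of participants is assumed throughout.

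On those terms the false-positive rate runs from 6–8% (7.84% rate, period odds ratio 1.5) to 9–21% (period odds ratio 2.27) over splits from 60/40 to 70/30, and 6–10% at 95% uptake. A reader might infer that the primary result will be wrong or will favour a particular strategy. The documents do not support that, since neither the size nor the direction of any bias can be known from them. The point is a cheap improvement.

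**What to change.** Add a period indicator (before vs after the cross-over) to the primary logistic model, and to the reach and service-delivery models:

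logit(p) = strategy + site + period + substance use + testing history.

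All four site-by-period cells are planned, so the strategy effect can be estimated. Site and strategy together identify the period, so no further data item is needed; the documents do not state that enrolment date is recorded. Keep the time-stratified analysis as descriptive.

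State the limit as well. With two sites and two periods, the period term uses the site-by-strategy contrast. A strategy effect that differs by site, or between the versions before and after PDSA, cannot then be separated from period or site effects.

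**Cost.** One line in the analysis plan, plus some precision if the sites are unequal. At a 7.84% rate and odds ratio 2.27 with no period change, Wald power is 80% without the term. With it, power is 80% at 50/50, 79% at 60/40, 77% at 65/35 and 73% at 70/30. The power statement in section 4.2 should note that unequal sites would take it below 80%.

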Recruitment of testing participants. Testing participants will be recruited in one of two ways: chain referral and credible messenger. In the chain referral strategy, an initial set of n=8 “seed” participants are recruitment by staff of eligible clients receiving services at Argus and Alliance (n=16 total seeds). For clinic-based recruitment of “seeds”, participants will be recruited from among those individuals who use opioids and other drugs who are receiving services through Argus or Alliance; services do not need to be substance use related. (Following a brief training, these “seed” participants then recruit additional participants (“peer recruits”) from among their own peer networks of those known to use opioid or other drugs in community settings (peer- recruitment). “Seed” participants are given three unique, numbered coupons, which they can give to people they know (peers) who are also use opioids and other drugs. The coupons will have information, by which peers who are interested in participating in the study can contact the research team to be screened for eligibility. Participants will receive renumeration for each peer recruit who enrolls in the study by redeeming a coupon given to them by that participant. Peer-recruits then repeat the same process with members of their peer network.

The credible messenger strategy involves leveraging the existing infrastructure at both Argus and Alliance, which includes credible messenger programs that are well-established, with considerable influence and impact within the respective communities served by these two agencies. The credible messengers within these programs have been trained to conduct community outreach to target individuals at increased risk for HIV, STIs, HCV and SUD and encourage testing and/or linkage to services. Interested credible messengers (n=4 from each site) will serve as messengers in the current study and will be trained to also include education about COVID-19, ways to reduce risk as well as ways to increase motivation to test for COVID-19 at the respective clinics. Credible messengers will conduct community outreach, targeting those locations and venues where potentially credible participants are located, and will provide education and encourage these individuals to seek testing. The potential participants will be given a coupon which will be redeemed at the clinic when the participant is enrolled in the study after being determined as eligible.

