Staff surveys. At the beginning of Phase 2, staff and credible messengers will complete brief surveys. Guided by EPIS, Andersen and SCT, surveys will collect data on theoretically-defined inner-, outer-, and individual-level factors that may influence the implementation of the recruitment strategies and testing. Surveys will capture demographics and professional history, and attitudes and knowledge regarding COVID-19, risk reduction behaviors and testing. Surveys will be available in paper/pencil format as well online via Redcap link; surveys will be administered again at the end of Phase 2 with similar content as well as items on palatability and felt-utility of the different strategies.

Test participant surveys. Following consent and study enrollment, all participants will complete a brief assessment consisting of structured survey examining predisposing and enabling factors (e.g. mental health, substance use, social support/capital), social-cognitive factors (COVID-19 attitudes, knowledge perceived risk, stigma) and structural variables (e.g. housing security; food insecurity) and a social network inventory. A social network inventory will be adapted from previous inventories.^{1,2} The inventory will consist of a set of standard “alter generators,” which are questions asking participants to list names, pseudonyms or initials of individuals within their social networks (“alters”) who fit certain descriptions (e.g. friends, loved ones, drug sharing partners, people who provide material support, etc.). Once alters have been generated and listed in an anonymized fashion, additional questions are asked about each alter to assess their age, frequency of interaction and duration of the relationship. Participants will also be asked about alters’ drug use, as well as previous disclosures of COVID-19 exposure or seropositivity between the participant and his/her alters. RAs will conduct interviews in private rooms at either Argus or Alliance locations. At the end of this survey the participant will receive COVID-19 testing; brief follow-up interviews will occur for those participants included in the chain-referral recruitment strategy when they return to receive compensation for redeemed coupons.

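### Section 4.5.2 adjusts the reach comparison for baseline measures that exist only for people who enrolled, so the strategy contrast cannot be estimated per coupon or recruiter and may be biased where it can be computed

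*Combined protocol and SAP*

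**What the plan says.** Section 4.5.1 defines the outcome: "An important secondary outcome will be reach measured through the number of coupons redeemed". Table 5 (section 4.3) gives the same count, adds redeemed over distributed as a secondary form, and types reach as primary. Section 4.5.2 then places reach with testing uptake and service delivery under one adjustment rule: "outcomes related to reach, testing uptake, and service delivery will adjust for measures assessed at baseline (e.g., baseline substance use, testing history".

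The logistic equation in 4.5.2, with terms for strategy, site, substance use and testing history, is written for testing uptake. For secondary outcomes the section says only that the model will be adapted, without naming a unit, distribution or link. Section 4.4.1 mentions reach in parentheses beside the logistic form.

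On timing, section 2.5 says that a person approached by a messenger "will be given a coupon which will be redeemed at the clinic when the participant is enrolled in the study". In chain referral, too, a coupon counts when the peer enrols with it. Section 3.1.1(b) says of testing participants: "Following consent and study enrollment, all participants will complete a brief assessment". Section 3.1.2(a) has Healthix consent, the route to prior testing records, sought from testing participants at enrolment. Staff and messengers get a different instrument: "Surveys will capture demographics and professional history, and attitudes and knowledge regarding COVID-19, risk reduction behaviors and testing".

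**The concern.** A covariate can adjust a comparison only if it is known for units with and without the outcome, and in both arms. Here the named covariates become known through the event being counted. The adjusted reach model therefore either has no information on the strategy contrast or must be moved to a unit where the covariates describe the people who make up the count.

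Reach is the first element of the hypothesis in 4.4.1 that chain referral does better. An analyst following 4.5.2 literally would get a failed fit, or would have to choose a unit after seeing the data. A model that does run could return a strategy effect distorted by the adjustment.

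**Working it through.** **The plan's own figure.** The documents give no sample size or power for reach. Section 4.2 covers testing uptake only: "recruit 500 participants in total (250 recruited in each strategy", "We also assume alpha (type I error rate) of 0.05" (sidedness not stated; two-sided assumed), and "the average baseline testing in the communities of interest (i.e., northern Manhattan, the Bronx) is 7842.2/100,000" against 16.1%.

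- Power = Φ{[d − 1.96·√(2p̄(1−p̄)/n)] / √([p₁(1−p₁)+p₂(1−p₂)]/n)}, with n = 250, p₁ = 0.078422, p₂ = 0.161, d = 0.082578 and p̄ = 0.119711.
- Numerator: 0.082578 − 1.96 × 0.02904 = 0.02567. Denominator: 0.02880. Ratio: 0.891, so power = 81.4%.
- Odds ratio: (0.161/0.839)/(0.078/0.922) = 2.27.

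Both agree with section 4.2. Neither bears on reach.

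**Who has the covariates.**

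| Person | Substance use | Testing history |
|---|---|---|
| Enrolled participant (coupon redeemed, or a seed) | Yes, survey after enrolment | Yes, survey or Healthix after consent |
| Holder of an unredeemed coupon | No | No |
| Chain-referral recruiter | Yes, as an enrolled participant | Yes |
| Credible messenger (4 per site, 8 in total) | Not in the listed content | Not clearly in the listed content |

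**Coupon level.** Let R = 1 if a coupon is redeemed. The covariates are observed only when R = 1, so the share of complete cases with R = 1 is 100%. The outcome is constant and no coefficient, including strategy, can be estimated. Using the distributor's covariates in place of the holder's turns this into the next case.

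**Recruiter level.** The linear predictor has 5 columns: intercept, strategy, site, substance use and testing history. Up to 250 chain-referral recruiters have complete data; with the listed survey content, 0 of 8 messengers do. Among complete cases the strategy column equals the intercept, and the checked matrix has rank 4 of 5. Strategy is not estimable. If the same covariates were collected from messengers, rank would be 5, but one arm would rest on 8 people.

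**Site-week level.** Assume 34 weeks at 2 sites (68 site-weeks), 500 enrolments spread evenly, and covariates averaged over each week's enrollees. In 500 simulated data sets a Poisson model had full rank 5 and converged 500 times, so estimability is not the defect here. The covariates summarise the people counted in the outcome. If a strategy brings in people with different drug use or less prior testing, those averages are a consequence of strategy, and conditioning on them can shift the strategy coefficient either way. A week with no redemption also has no average and drops out.

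**What a design-only comparison can support.** Two sites by two periods gives 4 site-periods. Intercept, strategy, site and period are 4 parameters, so residual degrees of freedom are 4 − 4 = 0. Splitting into weeks does not add site-periods. The mean standard error of the log rate ratio in the simulation was 0.091, close to √(1/250 + 1/250) = 0.089, the pure Poisson value. It contains nothing for variation between site-periods.

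**The case against.** The best defence is that 4.5.2 is flexible. Substance use and testing history are offered as examples, the equation is given for testing uptake, and adaptation is promised for other outcomes. This stands in part. A reader might infer that the model fails because 4 site-period counts cannot carry 5 parameters, but that applies the testing-uptake equation unadapted, in a unit the plan never names. The sentence on adjustment, however, names reach expressly, and adaptation of the model does not supply covariates for people who never enrolled.

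A reader might also infer that the adjusted model cannot be fitted in any unit. The site-week result shows otherwise. Nor are the covariates known only after the relevant count: chain-referral recruiters complete the survey before their own coupons are redeemed, so for them the measures are legitimate predictors. The gap at that level is the messengers. Their survey instrument is not shown, and the mention of testing could include their own history; demographics, which are collected, could be adjusted for.

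Section 3.1.1(a) also describes reach as recruitment of the target population, and a participant-level measure of that kind among enrollees could take baseline covariates. That stands, so the point is limited to the coupon count and redeemed/distributed, the only reach measures defined in 4.5.1 and Table 5.

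Finally, one might compare redemptions per recruiter directly, which would look lopsided because so few messengers distribute coupons. The plan proposes no such unadjusted model, so this says nothing about covariate adjustment.

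**Conclusion.** The concern holds in this form. For reach as defined, adjustment for participant baseline measures gives no strategy contrast at coupon level (100% of complete cases redeemed) or at recruiter level (complete cases from one strategy only). Where it can be computed, it conditions on characteristics that strategy may change.

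The recruiter-level result assumes that the survey content listed in 3.1.1(b) is what messengers are asked. The bias at site-week level is possible rather than shown: the documents give nothing from which to derive its direction or size.

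It would go too far to say that reach cannot be answered. Coupon counts and redeemed/distributed can still be reported without these covariates. Testing uptake, its adjustment and its power are not touched.

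**What to change.** In 4.5.2, remove the coupon count and redeemed/distributed from the outcomes adjusted for participant baseline measures. Compare both by strategy using design factors only (site and period). Each site runs one strategy per period, so site and strategy place a coupon in its site-period without needing redemption dates.

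State that only four site-periods underlie the comparison, show the four counts, and do not treat weekly counts within a site-period as independent. With no residual degrees of freedom at that level, the strategy ratio should be read largely descriptively. If recruitment closes at the target of 250 per strategy, which the documents do not say, report that too, since the count would then partly reflect the target.

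Report substance use and testing history of those reached as a descriptive profile by strategy. Keep covariate adjustment for testing uptake.

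The cost is a change of analysis-plan wording and a simpler analysis, with no new data. The downside is that reach is reported without case-mix adjustment. Collecting the same covariates from messengers would be an alternative, but with 8 of them it would be weak.
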